The standard care for the control arm will be: the LACDHS Vaccine Hesitancy Outreach Group calling patients once every month to remind patients of the need to be vaccinated and tested if needed. During the duration of the six weeks, the study participants will be exposed to the call from the LACDHS Vaccine Hesitancy Outreach Group.

Participants will receive two phone calls six-weeks apart, where they will complete a pre-survey in the first phone call, and 2 surveys (post-survey and CDE survey) in the second phone call. The survey will measure their trust in medical institutions, rate their self-efficacy, and intention, knowledge, and perceptions on COVID-19 testing and vaccination. Each survey will take about a half hour to complete, with the total time commitment for participants in Group 1 is about 1-1.5 hours. A copy of the surveys will be sent to the study participant either by email (preferred) or postal mail, prior to the telephone call.

An outline of the activities in Group 1 will look like:

1. Complete the pre- survey
2. Wait 6 weeks, where the LACDHS Vaccine Outreach Group will call one time in the month to remind them about getting the vaccine
3. After the 6 weeks have passed, the study staff will follow up with the participant to complete the post-survey and the CDE survey.

Study staff will use the REDCap Calendar feature to track events (such as when to administer the pre- and post- surveys) and will be used for data entry. The filters and reminders on the calendar feature assist study staff with adding events to adhere to study follow up times for study staff to call participants six-weeks later. If participants do not answer the phone calls to complete the post-survey, we will add a note on the patient’s chart, follow up three times to provide additional opportunities for patients to complete the study, and mark the patient’s chart as “Incomplete”. Once phone calls and post- surveys are complete, study staff will mark the participants’ charts as “Complete.”

Intervention Arm - CHW-led curriculum (Group 2)

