- **Pre- surveys** will be administered by IRB-approved study staff, after study participants are consented and enrolled into the study and at a convenient time for the study participant. The survey should take about 30-60 minutes to complete (**see Pre- and Post- RADxUP Survey**). The survey questions and answers will be sent via email or mail prior to the phone call, and read and answered over the phone by the study staff to overcome any misinterpretation of the survey questions. The participant's response will be input by the study staff directly into REDCap under the subject ID#. No special training will be required to administer the survey.
- **Post- surveys** will take between 30-60 minutes to complete (**see Pre- and Post- RADxUP Survey**). The survey questions and answers will be read and answered over the phone by study staff to overcome any misinterpretation of the survey questions. The participant's response will be input by the study staff directly into REDCap under the subject ID#. No special training will be required to administer the survey.
 - o The post survey will be administered by study staff telephonically (similar to the pre-survey process) after:
 - Control arm – 6 weeks from the first survey
 - Case arm – after they complete the 6th group class and 6th personal phone call with the CHW

As part of the intervention arm, the modules will incorporate weekly formal “Knowledge Checks” (**see Knowledge Checks**) a comprehension questionnaire administered via email survey (sent by REDCap) sent after each module, which all participants will complete before their personal phone call with the CHW. The purpose of these Knowledge Checks is for the study team to measure patients' comprehension after each group session and throughout the course of the study. If patients score low in the Knowledge Checks, the CHW will review with the patients during their personal sessions to increase comprehension of the materials presented during the group session. There will be a total of 5 Knowledge Checks for Modules 1-5 (the Post- survey will be administered in lieu of a Knowledge Check for Module 6), each with 5-10 multiple-choice questions.

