CDE Survey - The questions on this survey are required to be collected, as noted in the NIH's terms and conditions of funding the project. The project staff is in the process of requesting an exemption review for the Alcohol and Tobacco questions. However, the CDCC instructed the project staff to include all of the Common Data Elements as created by the NIH until our request is reviewed and approved. Selected CDE questions are used in the basic demographic survey that will be asked once (See Basic Demographic Survey). Additional information about the CDE's and a copy of the CDE survey can be found on the RADx-UP website at: <https://radx-up.org/learning-resources/cdes/>

Due to the sensitive nature of select questions, the study team will provide this survey to the study participants at the end of the project to give the project team additional time to have the questions reviewed and approved to be exempted. The study staff will notify the participants during the consent they will have to complete this additional survey at the end of the project. The survey will be sent out via REDCap to the participant's email and explain to participants they are also given the option to not answer any questions they do not want to answer. The answers to the survey will be saved on REDCap and shared via a secure portal to the NIH's RADxUP data sharing hub.

Pre- survey – will be administered telephonically with study staff after the study participant is consented and enrolled in the study, at a time that is convenient for the study participant. The study staff, who are IRB approved, will send the survey to the participant to review prior to data collection, and will read the questions and answer choices aloud and input the participant's answer directly into REDCap under the Subject ID#. If participants state they are comfortable with completing the survey on their own, the study staff will send the survey via REDCap to the email. Participants enrolled in both control and case arm will complete this survey. Participants in the case arm will complete the survey before they attend the group classes and phone calls with the CHW.

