Post- survey – like the pre- survey, the post- survey will be administered telephonically with study staff, at a time that is convenient for the study participant. The study staff, who are IRB approved, will resend the survey out before the phone call to read the questions and answer choices aloud and input the participant's answer directly into REDCap under the Subject ID#. Participants enrolled in both control and case arm will complete this survey. Participants in the control arm will complete the post- survey 6 weeks after they complete the pre- survey. Participants in the case arm will complete the survey after they attend the 6th group class and 6th phone call with the CHW.

Knowledge checks – this survey will only be administered to study participants randomly assigned to the case arm on a weekly basis, after they attend a group session. The survey will be sent out via email using the REDCap survey feature. If participants are not able to complete the survey via email, study staff will follow up with the participants via phone call to complete the survey where study staff will read the questions and answers aloud. The

study staff will then enter the answers directly into REDCap. This survey will need to be completed before the participants complete their personal phone calls with the CHW.

Patient encounter forms – this data collection tool will only be used on study participants randomly assigned to the case arm during their weekly teleconsultations. Intervention CHWs will complete these forms after each of their teleconsultations (personal phone calls) with their assigned study participants and enter their notes on REDCap. Each participant will have six completed patient encounter forms in their subject file on REDCap by the end of the study. The teleconsultations will be scheduled at a time that is convenient for both the participants and the CHWs.

One of the MPI and software programmer will strip personally identifiable information from the clinic data and substitute with a random code (Subject ID#). A master code list will be created separately that will link the code with the patient. This master code list will reside in a separate file in REDCap.

b. Where will the data be stored and how will it be secured during the study?

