Aim 3 - After data cleaning, we will assess psychometric properties of all scaled measures, calculate descriptive statistics to ensure quality of the data (check distributions, examine outliers) and to describe study participants. Bivariate analyses will include independent t-tests models (or their nonparametric equivalents, e.g. Wilcoxon rank-sum test, differences between the groups in trust and self-efficacy. Paired-tests (or Wilcoxon signed-rank test) will be used to assess change within groups. Contingency table analyses will address intention to participate in COVID-19 testing and vaccination. We will then fit multiple regression models predicting change in COVID-19 testing- and vaccine-related knowledge, trust, and self-efficacy as a function of intervention group, racial/ethnic group, and possible interactions. We will use covariate adjustment approaches such as multiple linear and logistic regression models for the three outcomes (trust, self-efficacy, intent to participate) while controlling for demographic characteristics (e.g. age, gender, education, health status) and other potential covariates that will be identified a priori. We do not anticipate many missing data, given the format of completion. However, if we do have 10% or more missing, we will impute data using SAS PROC MI and SAS PROC MIANALYZE to implement these multiple imputation procedures. With respect to sample size, with 64 subjects in each of the two study groups, it will be possible to detect an effect size of 0.5 standard deviations in a quantitative outcome (a medium effect size in Cohen’s terminology) with 80% power and 2-sided 5% significance level.

VII. Funding

4. Check all types of funding sources for this study.

 Federal Grant/Contract  State, Local Government  International	 Private  Internal Grant Program  Departmental
--	--

 Industry	 Other:
2. Name of Funding Source (e.g. NIH)	NIH/National Library of Medicine
3. Grant/Contract Title*	A Community Health Worker Intervention to Identify and Decrease Barriers to COVID-19 Testing and Vaccination among Los Angeles County Department of Health Safety-Net Patients (Title of the Supplement to parent R01)

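### The protocol lets some participants self-complete the pre-survey online but has the post-survey read to them by telephone, so their pre-post change includes a change of survey mode.

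*Protocol*

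**What the plan says.** All references are to section VI of the protocol.

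- **Pre-survey, item 10.a (Data Collection).** Telephone with study staff is the default, followed by an opt-out: "If participants state they are comfortable with completing the survey on their own, the study staff will send the survey via REDCap". The paragraph applies to both arms.
- **Pre-survey, item 9 (Surveys).** Questions are "read and answered over the phone by the study staff to overcome any misinterpretation of the survey questions". No self-completion is mentioned.
- **Pre-survey, item 8 (Control Arm).** "Participants will receive two phone calls six-weeks apart, where they will complete a pre-survey in the first phone call". Again, telephone only.
- **Post-survey, item 10.a.** "like the pre- survey, the post- survey will be administered telephonically with study staff". Staff "will resend the survey out before the phone call to read the questions and answer choices aloud". The opt-out is not repeated.
- **Post-survey, item 9.** Items are "read and answered over the phone by study staff to overcome any misinterpretation of the survey questions", in both arms.
- **Order of events, item 8.** Participants consent, complete the demographic survey, are randomised and are told their group. The procedures for each group then begin with the pre-survey.
- **Analysis, item 25.** Paired tests or signed-rank tests "will be used to assess change within groups". Regression models predict change in knowledge, trust and self-efficacy from intervention group. Intent is handled by contingency tables and by the covariate-adjusted models for the three outcomes. No listed analysis refers to survey mode.

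**The concern.** A pre-post comparison assumes that the instrument measured the same thing in the same way both times. The outcomes here are attitudes and self-ratings, and answers to a live member of the study staff can differ from answers to a web form. The protocol itself treats mode as relevant: its stated reason for reading the questions aloud is to prevent misinterpretation. A self-completer lacks that help at baseline and has it at follow-up.

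For such a participant the difference between the two scores is real change plus a mode shift. A paired test within an arm attributes all of it to change. The regression of change on intervention group takes in the same contaminated scores, and could be distorted if the contamination is unequal between arms.

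**Working it through.** **1. The plan's own figure.** For 0.5 SD, two-sided 5% and 80% power, the normal approximation is n = 2(1.96 + 0.842)² / 0.5² = 62.8, so 63 per arm. With the stated 64 per arm, power is 80.7% (normal) or 80.1% (noncentral t). The stated sample size reproduces and does not depend on survey mode.

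**2. Do the passages allow a switch?**

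| Survey | Item 8 (control arm) | Item 9 | Item 10.a |
|---|---|---|---|
| Pre | telephone | telephone | telephone, or self-completed by REDCap on request |
| Post | telephone | telephone | telephone |

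Item 10.a disagrees with items 8 and 9 on the pre-survey. Under item 10.a as written, a participant who opts out at baseline has no stated opt-out at follow-up. Even if the option were meant to carry over, nothing holds a participant to the same mode twice.

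**3. Within-arm shift.** Let m be the mode effect in SD units of the score and p the share who self-complete at baseline. The spurious mean change in an arm is m × p. The protocol gives neither value, so both are assumptions, as is the direction.

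| m | p = 10% | p = 25% | p = 50% |
|---|---|---|---|
| 0.1 SD | 0.010 | 0.025 | 0.050 |
| 0.2 SD | 0.020 | 0.050 | 0.100 |
| 0.3 SD | 0.030 | 0.075 | 0.150 |

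**4. Effect on the paired test.** With 64 per arm and an assumed pre-post correlation r, the SD of change is √(2(1 − r)): 1.00 at r = 0.5 and 0.775 at r = 0.7. The noncentrality is √64 × shift / SD of change. For a shift of 0.10 SD this is 0.80 or 1.03. With no true change, a nominal 5% test then rejects at these rates:

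| Shift | r = 0.5 | r = 0.7 |
|---|---|---|
| 0.025 SD | 5.4% | 5.7% |
| 0.05 SD | 6.8% | 8.0% |
| 0.10 SD | 12.4% | 17.4% |
| 0.15 SD | 21.9% | 33.2% |

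**5. Randomised contrast.** With uptake p₁, p₀ and mode effects m₁, m₀ in the two arms, the bias in the difference in mean change is m₁p₁ − m₀p₀. With equal uptake and equal mode effect it is exactly 0. With a common m and a 25-point difference in uptake (an illustration, not a forecast):

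| m | Bias | Share of 0.5 SD | Rejection with no true effect |
|---|---|---|---|
| 0.1 SD | 0.025 SD | 5% | 5.2% to 5.4% |
| 0.2 SD | 0.050 SD | 10% | 5.9% to 6.5% |
| 0.3 SD | 0.075 SD | 15% | 7.1% to 8.4% |

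The ranges in the last column cover r = 0.5 to 0.7.

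**6. Could uptake differ by arm?** Item 8 places the pre-survey after group notification, so the participant can choose a mode knowing the arm. That makes a difference possible. Nothing in the protocol shows that there will be one, or in which direction.

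**The case against.** Telephone is the default everywhere, and self-completion is an opt-out in one sentence. Only those who take it can switch mode, and the number may be small: at 10% uptake and a 0.1 SD mode effect the shift is 0.01 SD. The post-survey is also introduced as being conducted in the same manner as the pre-survey, which might mean that the option carries over. These points stand as limits on size and certainty. They do not remove the conflict between item 10.a and items 8 and 9, or the lack of any rule holding a participant to one mode.

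A reader might infer more than the documents support:

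- **That the treatment effect is biased.** Both arms follow the same survey rules, so an equal shift cancels. Comparisons of post-survey levels use one mode throughout on the plain reading, and baseline mode would enter them only through adjustment for the baseline score.
- **That change in intent is affected in the same way.** Item 25 does not list intent among the regressions of change.
- **That interviewers' knowledge of the arm is part of this problem.** Study staff tell participants their group and no blinding of interviewers is described. That risk would exist with telephone at both times and is a separate matter.
- **That self-completion should become the default.** That would give up the stated reason for reading items aloud, in a population for which the protocol names access to health technology as a barrier. The Knowledge Checks, also sent by REDCap, already need a telephone fallback.

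**Conclusion.** The point holds in a limited form. The protocol contradicts itself on how the pre-survey is given and, followed as written, changes the mode for anyone who self-completes at baseline. The clear consequence is for the within-arm paired tests, which cannot tell that switch from real change. Under assumed mode effects of 0.1 to 0.3 SD and 10% to 50% uptake the shift is about 0.01 to 0.15 SD per arm: negligible at the low end, and enough at the high end to raise the paired test's false-positive rate well above 5%. The effect on the randomised comparison is zero unless uptake or mode effect differs by arm, which the order of events permits but nothing shows. Mode effect, uptake, direction and pre-post correlation are all assumptions. The sample size is unaffected. It is worth correcting because analysis could not cleanly undo a mixed baseline later.

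**What to change.** Reconcile the control-arm procedures in item 8, the pre- and post-survey paragraphs in item 9 and those in item 10.a, so that each participant uses the same mode at both surveys. Either of two changes does this:

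1. Delete the self-completion sentence in item 10.a, leaving telephone at both times.
2. Keep the option, but settle each participant's mode before the arm is announced, use it at both surveys, and say so in all three items. Suggested wording: *The mode chosen before group notification is used for both the pre-survey and the post-survey.*

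In either case, add a REDCap field for the mode actually used at each survey, so that any departure is visible.

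The cost is a few sentences and one field. Under the first change some participants lose a convenience; under the second, self-completers may need a reminder call. Neither changes the sample size or the analyses in item 25.

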The potential benefits of the research must justify the risks to research participants. The risk/benefit ratio of the research must be at least as favorable for the participants as that presented by standard treatments for their condition. When comparing the risk/benefit ratio of research with that of available alternatives, the alternative of doing nothing should be included in the analysis.

The risk/benefit ratio of this research is favorable, because this is a low risk study and we aim to minimize the risk in several ways, (e.g. limiting who has access to the data, the use of REDCap to collect data, the use of unique study ID# on the participant's data and keeping the master code list in a separate, secure location). While there is no direct benefit to the individual participant, there may be a benefit to society in that the information gained in the study. Findings from this study may help identify barriers to COVID 19 testing, vaccination, and health care for African American and Latino patients in the Los Angeles County Department of Health Services, which may also inform the challenges faced by African American and Latino patients in similar County health care systems in other cities. The risks to the participants are reasonable in relation to the importance of knowledge to be gained.

Financial Considerations

17. Payment for Participation: Describe all plans to compensate participants, including provision of services, and other reimbursements. Describe the conditions that participants must fulfill to receive full or partial payment.

Study participants in the case arm will receive a \$599 compensation (71 participants), and study participants in the control arm will receive \$100 compensation (71 participants) for their time and effort.

Control arm:

Participants in the control arm will be compensated with a \$100 gift card at the end of the study, after they complete the basic demographic, CDE, pre- and post- surveys. If the participant starts the surveys and cannot complete the required pre-, post-, and demographic surveys, then the participant will get the partial payment of \$50.

Case arm:

Participants will be compensated in weekly installments, after completing the first week of the 6-week program, the participant will receive a \$99 gift card, and subsequent weeks with \$100 gift cards for every successful week of completion (group session and personal session with CHW).

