If the participant cannot complete participation requirements for the case arm of the study for any given week (completion of the group session and personal session, or if the study personnel decides that the participant cannot continue), then the participant will get the partial payment of \$50. If the participant drops out the study, they will not receive further payment.

18. Financial Obligations of Participants: Will participants have to pay for any of the tests or treatments that they receive as part of the research? *Please clarify who will pay for the procedures associated with the study as well as procedures that may be part of standard clinical care. Clarify that insurance and other third party payers may not cover standard procedures if they are associated with a research project.*

The participants do not have to pay to take part in this study. There are no financial obligations to the participants.

19. Emergency Care and Compensation for Research-Related Injury: If the research presents a greater than minimal risk, the financial liability for the costs of care associated with potential research related illness/injury must be specified. *(if no funds are available, please see the consent form template for the standard language to explain this to potential participants)*

Not applicable. This study is minimal risk.

Informed Consent

If you are requesting (1) waiver or alteration of consent, (2) waiver of parental permission, or (3) waiver of documentation of consent, please attach Form 115 to this application.

20. Capacity to Consent: Will all participants have the capacity to give informed consent? If not, describe the likely range of impairment and explain how, and by whom, their capacity to consent will be determined.

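### Payment, timing and follow-up tie the post-survey to programme completion in the intervention arm only, which risks outcome data going missing differently by arm

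*Protocol*

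**What the plan says.** Three parts of the Protocol decide whether a patient's post-survey is obtained.

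**Payment (item 17).** Control patients receive $100 at the end of the study, "after they complete the basic demographic, CDE, pre- and post- surveys". The reduced amount of $50 applies "If the participant starts the surveys and cannot complete the required pre-, post-, and demographic surveys". Intervention patients are paid by the week: $99 for week 1, then $100 "gift cards for every successful week of completion (group session and personal session with CHW"). A payment of $50 applies "If the participant cannot complete participation requirements for the case arm of the study for any given week", and the requirements listed there are again the two sessions. The section ends: "If the participant drops out the study, they will not receive further payment". No survey is named as a payment condition in the intervention arm.

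**Timing (item 9, repeated in item 10a).** The post-survey is due as follows: "Control arm – 6 weeks from the first survey"; "Case arm – after they complete the 6th group class and 6th personal phone call with the CHW".

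**Follow-up of non-responders (item 8).** The description of the control arm provides for three further attempts when a patient does not answer the post-survey call. The description of the intervention arm has no such provision.

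Item 9 makes the pre- and post-surveys the source of the three key measures in both arms: trust, self-efficacy and intent.

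**The concern.** The trial compares arms on answers given in the post-survey. In control, the survey is due on a date, has money attached and is chased. In the intervention arm it is due on an event (finishing the programme), comes after the last paid activity, and is not stated to be chased.

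Patients who lose interest in the classes are plausibly those with lower trust in the health system or weaker intent, and these are the outcomes. If their surveys are missed more often than those of comparable control patients, the observed intervention group is no longer the randomised group, and randomisation does not protect against that. Item 25 plans multiple imputation if 10% or more is missing. Imputation that assumes data are missing at random recovers only the part of the loss explained by recorded variables, not loss driven by the unseen post-study answers.

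**Working it through.** **1. Payment arithmetic (item 17).** Intervention: 99 + 5 × 100 = 599. This reproduces the stated $599, so the sessions use up the whole amount. Control: 100 − 50 = $50 depends on finishing the surveys.

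| | Control | Intervention |
|---|---|---|
| Maximum payment | $100 | $599 |
| Part that depends on finishing the surveys | $50 | $0 |
| Paid when requirements are not met | $50 if surveys started | $50 for a missed week |
| After drop-out | no separate rule | nothing further |
| Post-survey due | 6 weeks after pre-survey | after 6th class and 6th call |
| Three follow-up attempts written | yes | no |

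**2. The Protocol's own size figures.** With 64 per arm, 0.5 SD and two-sided 5%, power from the noncentral t distribution is 80.1%, matching the stated 80% (item 25). With 142 recruited and 10% loss, 142 × 0.9 = 127.8, in line with the required 128. The attrition allowance is about 10% in each group, so the plan assumes equal loss. These figures are not in dispute.

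**3. Bias illustration.** The Protocol gives no arm-specific loss rates, so every input here is an assumption. Let *m* be the share of an arm without a post-survey, and *g* the amount, in SD, by which those patients would have scored below the completers of that arm. The true arm mean is the completer mean minus *m* × *g*, so the completers overstate the arm by *m* × *g*. The bias in the difference between arms is

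bias = m_I × g_I − m_C × g_C.

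- Equal 10% loss and equal *g* = 0.5: 0.10 × 0.5 − 0.10 × 0.5 = 0.
- 20% intervention loss, counting that arm only: 0.20 × 0.25 = 0.05 SD; 0.20 × 0.5 = 0.10 SD.
- 30% intervention loss, counting that arm only: 0.30 × 0.25 = 0.075 SD; 0.30 × 0.5 = 0.15 SD.
- 20% intervention loss and 10% control loss, same *g* in both arms: 0.25 × (0.20 − 0.10) = 0.025 SD; 0.5 × (0.20 − 0.10) = 0.05 SD.

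Against the 0.5 SD target, 0.05 to 0.10 SD is 10% to 20%. If *g* were negative in the intervention arm (non-completers scoring higher), the sign would reverse. The figures are for a complete-case comparison.

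**4. Power illustration.** With 71 randomised per arm, 10% control loss (64 left) and intervention loss of 10, 20, 30 or 40% (64, 57, 50 or 43 left), power at 0.5 SD is 80.1, 77.7, 74.7 or 71.0%. The loss of power is modest; the possible bias matters more.

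**The case against.** **The post-survey may be part of the paid programme.** Item 9 says that "the Post- survey will be administered in lieu of a Knowledge Check for Module 6", item 8 counts two half-hour phone calls in the 20-hour commitment, and the $599 is described as compensation for time and effort. The survey could therefore be read as belonging to week 6. This shows that the wording could be clearer, but item 17 defines a completed week by the group and personal sessions alone. Even on the generous reading, a patient who left before week 6 is paid nothing for the survey.

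**Intervention retention may be the better of the two.** That arm has weekly contact with a community health worker, up to $599 against $100, and a tablet where needed, which the investigators expect to help retention. Control patients get $50 merely for starting the surveys. This stands: one cannot say from the Protocol which arm will lose more. None of these features, however, rewards the survey itself or reaches patients who have stopped attending.

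**Different burdens justify different pay.** Item 8 puts the commitment at 20 hours against up to 2. Agreed; the totals are not at issue, only what the money is attached to.

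**Stronger readings that the text does not support.** A reader might infer that an intervention patient who stops attending gets nothing more. Item 17 separates a missed week, which earns $50, from dropping out of the study, which ends payment. A reader might also infer that the results will be biased in favour of the intervention, or attach one figure to that bias. The direction rests on who fails to respond, which the Protocol does not tell us, and the size is zero under equal loss with equal deficits.

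**Conclusion.** The point holds as a design weakness. $50 in control and $0 in the intervention arm depends on finishing the surveys. The intervention post-survey is due on programme completion rather than on a date, and the follow-up attempts are written for control only. Together these link outcome collection to programme completion in one arm, which risks differential and possibly informative missing data on all three key outcomes.

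The size and direction of any bias cannot be derived from the Protocol. The illustrative range of 0 to about 0.10 SD rests on assumed intervention loss of 10 to 20% and an assumed deficit in non-completers of up to 0.5 SD. The zero requires equal loss and equal deficit in both arms; the 0.05 to 0.10 SD counts the intervention arm only. This is a cheap improvement worth making before data are collected, since outcomes not obtained cannot be recovered in the analysis. It is not evidence that the trial will mislead.

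**What to change.** - **Item 17:** pay the same amount for a completed post-survey (for example $50) to every randomised patient in both arms, regardless of attendance. In the intervention arm take it from the existing total: 599 − 50 = $549 left for sessions, or 549 / 6 = $91.50 a week if spread evenly. In control, the existing second $50 can serve.
- **Items 9 and 10a:** make the intervention post-survey due at a fixed time comparable to the control arm's six weeks, whatever the attendance. State the starting point of the count, because item 8 staggers the start of the intervention groups.
- **Item 8:** apply the three follow-up attempts to both arms, and say that they include patients who have stopped sessions but have not withdrawn from the study.

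The cost is a slightly smaller weekly session payment and a wording change in the Protocol and consent form. The $599 and $100 maxima do not change. Patients who stop sessions but answer the survey would now receive $50 each; if 14 of 71 did so, 14 × 50 = $700.
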